12.2 Missing, unused & spurious data

Any instances of unused or spurious data will be reported. If the quantity of missing data becomes an issue in this study, suitable analyses techniques will be used to impute data as required.

12.3 Procedures for reporting deviation(s) from the original protocol

Protocol deviations, non-compliances or breaches are departures from the approved protocol. Accidental protocol deviations can happen at any time. They must be adequately documented on the relevant forms and reported to the CTR. Deviations from the protocol which are found to frequently recur are not acceptable, will require immediate action and could potentially be classified as a serious breach. These will be reported by the PI to the CTR and will be followed up by the study manager.

12.4 Inclusion in analysis

All screened patients will be reported. For each analysis, only patients with relevant evaluable data will be analysed. Where relevant, differences between those with and without the relevant evaluable data will be reported as a check for bias.

13 Analysis

13.1 Main analysis

All analyses will report a proportion and 95% confidence interval. Where appropriate (i.e., if the proportion is <5%), the 95% confidence interval will be reported as per Wilson's method.

17

14 Data Management

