5.4 Secondary outcomes measure(s)

- The proportion of participants, over eight months from screened, eligible and willing to be randomised in a future trial to:
 - a. no treatment
 - b. topical treatment
 - c. a few days of oral antibiotics
 - d. a week of oral antibiotics
- The proportion of participants recruited over eight months from eligible.
- The proportion of participants completing the study (responding to the postal questionnaire) over eight months from eligible.
- Assess feasibility of 'wound selfies' or wound photographs taken in the department as an objective outcome measure.
- The proportion of participants with SSI who were prescribed oral antibiotics at the time of surgery.
- Ulcerated tumour swab analysis results

6 Study design and setting

Clinicians in the dermatology department will identify eligible participants at the time of initial consultation in outpatient clinic.

Identification of potential participants will be by the clinical care team, or the clinical members of the research team involved in care of potential participants. Potential participants will be signposted to the research team by the clinical care team.

Patients will be approached by a trained member of the clinical team or research nurse following clinical checks against the inclusion and exclusion criteria. They will be provided with an information leaflet and any other information about the study they request. The patient will be given sufficient information to ensure they fully understand the nature and risks of the study and are given as much time as they require to consider their participation. If they are willing to participate, they will be consented and admitted to the study at the time of surgery. Prior to the procedure relevant clinical information will be recorded in the Case Report Form (CRF) including demographic data, tumour site, tumour size, and size of tumoural ulceration. Participants will be asked whether they would prefer to be contacted via post or e-mail with

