11.3 Skin swabs (CAVUHB participants only)

Participants enrolled to the study at the University Hospital of Wales, Cardiff will have swabs of ulcerated skin tumours taken and analysed in the Public Health Wales laboratory at the University Hospital of Wales, Cardiff.

It is the responsibility of the study site to ensure that samples are appropriately labelled in accordance with the study procedures to comply with the current Data Protection legislation. Biological samples collected from participants as part of this study will be transported, stored, accessed and processed in accordance with national legislation relating to the use and storage of human tissue for research purposes and such activities shall at least meet the requirements as set out in the 2004 Human Tissue Act.

Swabs of the ulcerated tumours will be taken with no prior cleaning prior to skin surgery. Completed swabs will be deposited in specimen collection baskets within the dermatology department and will be shipped to the laboratory via the standard portering system.

Swabs will be cultured onto a range of non-selective and selective media. Bacterial pathogens will be semi-quantified and identified using MALDI-ToF and other tests where applicable. Microbiological infection will be determined according to local Standard Operating procedures,

based upon UK national Standards in Microbiology Investigations (SMI) guidelines. After the skin swabs have been processed then they will be destroyed according to laboratory regulations.

The aim of this is to identify the most common organisms that grow in ulcerated tumours which will help to guide antibiotic choice in a future randomised controlled trial.

Currently, there is no consensus on which antibiotic would be most appropriate to reduce the risk of surgical site infection in ulcerated skin tumours. This may be partly explained by the paucity of data regarding pathogens of ulcerated skin tumours. One single-centre study in Australia isolated *Staphylococcus aureus* in 93 of 97 ulcerated lesions and gram-negative bacteria (including *Klebsiella*, *Acinetobacter*, *Proteus*, *Serratia* and *Escherichia* species) in 7 of 97 ulcerated lesions.¹⁶ However, it is not clear whether this was conducted in a research laboratory setting or in a clinical setting where the laboratory would aim to identify the presence of known skin pathogens.

12 Statistical considerations

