12.1 Sample size

Given the wide range in reported SSI from published case series between 2-33%, we anticipate a SSI of approximately 10% in our participants with ulcerated skin tumours. Our aim is to recruit 311 participants with an intended sample size of 283 participants (allowing for a dropout rate of 10%). This will give a 95%CI of between 6.9% to 13.5%.

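### Section 13.1 reserves Wilson's interval for proportions below 5% and names no method otherwise; one method should apply to every proportion

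*Combined protocol and SAP*

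**What the plan says.** The analysis section is two sentences long. The first sets the scope: "All analyses will report a proportion and 95% confidence interval". The second gives the only rule on method: "Where appropriate (i.e., if the proportion is <5%), the 95% confidence interval will be reported as per" Wilson's method. Neither that section nor any other names the interval to be used at 5% or above.

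Three other places bear on the rule.

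- **Section 12.1 (sample size).** The planning value is 10% ("we anticipate a SSI of approximately 10% in our participants with ulcerated skin tumours"), with an "intended sample size of 283 participants". On precision it says "This will give a 95%CI of between 6.9% to 13.5"%. No method is named.
- **Section 5.4 (secondary outcomes).** One outcome is "The proportion of participants with SSI who were prescribed oral antibiotics at the time of surgery". Read as a percentage among SSI cases, its denominator is a small part of the cohort. Swab results are another secondary outcome, and swabs are taken at Cardiff only.
- **Section 11.3 (skin swabs).** The background cites a study that isolated one organism "in 93 of 97 ulcerated lesions", a proportion close to 100%.

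**The concern.** A rule that turns to Wilson only for small proportions makes most sense if the default is the normal approximation, which is known to fail there. But that failure is not confined to small proportions. It is symmetric, so it occurs near 100% as well, and it depends on the number of events and non-events, so a small denominator can cause it at 7% or 10%. The rule looks only at whether the proportion is below 5%.

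Changing formula at a cut-point in the data adds a second problem: the two formulas need not join up, so the interval can move the wrong way as the count crosses 5%.

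At stake is the reporting of secondary outcomes, which are meant to inform the design of a later randomised trial. Limits below 0% or above 100%, or an interval of zero width, misstate the uncertainty that the later design has to allow for.

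**Working it through.** **Inputs.** n=283 and 10% come from 12.1. The denominator of 28 is 10% of 283 (28.3), for antibiotics among SSI cases. The denominator of 97 is that of the study cited in 11.3. The documents give no Cardiff denominator and no expected antibiotic proportion among SSI cases, so n=28 and n=97 are illustrations. z = 1.96.

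**Formulas**, with p = x/n:

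- Normal approximation: p ± z√(p(1−p)/n)
- Wilson: [p + z²/(2n) ± z√(p(1−p)/n + z²/(4n²))] / (1 + z²/n)
- Exact: Clopper-Pearson

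**Step 1: the plan's own interval.** At p = 0.10 and n = 283 the standard error is √(0.10 × 0.90/283) = 0.01783, and 1.96 × 0.01783 = 0.0350.

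| Method | 95% interval |
|---|---|
| Stated in 12.1 | 6.9% to 13.5% |
| Normal approximation | 6.5% to 13.5% |
| Wilson | 7.0% to 14.0% |
| Exact | 6.8% to 14.1% |

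None of the three reproduces the stated pair. The upper limit fits the normal approximation and the lower does not. Wilson at 28/283 gives 6.93% to 13.93%, which fits the lower limit only. So 12.1 does not reveal the default method.

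**Step 2: limits under the 13.1 rule if the default is the normal approximation.** Every count at or above 5% was checked.

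| n | Lower limit below 0% | Upper limit above 100% | Zero width |
|---|---|---|---|
| 28 | 2, 3 | 25 to 27 | 28 |
| 97 | none | 94 to 96 | 97 |
| 283 | none | 280 to 282 | 283 |

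For 2/28, p = 0.0714 and the standard error is 0.0487, so the interval is 7.14% ± 9.54 points. Examples:

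| Count | Normal approximation | Wilson |
|---|---|---|
| 2/28 | -2.4% to 16.7% | 2.0% to 22.6% |
| 26/28 | 83.3% to 102.4% | 77.4% to 98.0% |
| 28/28 | 100% to 100% | 87.9% to 100% |
| 93/97 | 91.9% to 99.8% | 89.9% to 98.4% |
| 97/97 | 100% to 100% | 96.2% to 100% |

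The cited result, 93/97, gives a possible interval. One more positive (94/97) does not.

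**Step 3: the switch at 5%.**

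| Count | Proportion | Method under the rule | Interval |
|---|---|---|---|
| 14/283 | 4.95% | Wilson | 2.97% to 8.13% |
| 15/283 | 5.30% | Normal approximation | 2.69% to 7.91% |
| 4/97 | 4.12% | Wilson | 1.62% to 10.13% |
| 5/97 | 5.15% | Normal approximation | 0.75% to 9.55% |

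In both pairs one more event lowers both limits.

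**Step 4: coverage**, by summing binomial probabilities over all counts whose interval contains the true value.

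| n | True proportion | 13.1 rule | Wilson throughout |
|---|---|---|---|
| 28 | 95% | 76.0% | 95.1% |
| 28 | 90% | 94.3% | 94.5% |
| 97 | 95% | 86.0% | 97.0% |
| 97 | 96% | 89.8% | 94.0% |
| 283 | 10% | 94.8% | 95.3% |
| 283 | 8% | 94.9% | 95.2% |

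At n=28 and true values of 5% to 15% the rule over-covers (98.4% to 99.8%).

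**The case against.** The strongest objection is that the normal approximation is never named. All the impossible limits, the zero widths, the low coverage and the reversal depend on it. If the intended default were exact, none of these would arise, and the only fault would be that the method is not stated. This stands as a caveat, and every figure in steps 2 to 4 of the working is conditional on it. It does not remove the gap: the method for the primary outcome, expected at 10%, is unspecified on any reading.

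Second, the opening words of the Wilson sentence might let the statistician use Wilson wherever the simple interval is unsuitable, including above 95%. The text is against this, because the bracket defines the condition as a proportion below 5%.

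Third, the problem cases may not occur. The n=28 case depends on how the antibiotic outcome is read, the n=97 denominator belongs to another study, and 11.3 itself questions that study's laboratory setting. Recruitment and completion should not come near 100%, since 9.3 assumes just under half agree and 12.1 assumes 10% dropout. All of this is fair, and it limits the size of the point. Near-100% results remain possible for swab positivity and for willingness to be randomised.

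Fourth, no secondary interval is tied to a test or a progression threshold, and an out-of-range limit would be noticed at reporting. True, but a poorly covering interval inside 0% to 100% would not be noticed, and choosing another formula at that stage would be a choice made after seeing the data.

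**Conclusion.** The concern holds, as a minor point about secondary reporting. It is certain that 13.1 names a method only below 5% and has no condition on denominator or on proportions near 100%. The numerical consequences assume a normal-approximation default, which is the natural reading but is not confirmed by 12.1. They also assume illustrative denominators of 28 and 97.

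For the primary outcome at 10%, the choice of formula moves each limit by about half a point and the sample size does not change. The reversal would touch the primary outcome only if observed SSI fell near 5%. That is inside the 2% to 33% range quoted in 12.1 but well below the planning value.

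**What to change.** Replace the second sentence of 13.1 with: *All 95% confidence intervals for proportions will use Wilson's method.* Restate the precision in 12.1 on the same basis at n=283: 7.02% to 14.05% at 10%, or 6.93% to 13.93% if written as 28/283.

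If an exact interval was the intended default, naming it for all proportions would also remove the impossible limits and the reversal (15/283 gives 3.00% to 8.59%). Wilson is the simpler edit because the plan already uses and references it.

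The cost is one sentence and one figure, with no extra patients or data. At 10% of 283 the Wilson interval is 7.03 points wide (14.05 − 7.02), against 6.99 for the normal approximation (2 × 1.96 × 0.01783 = 0.0699).

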14.1 Access to Data

Direct access will be granted to authorised representatives from the sponsor and host institution for monitoring and/or audit of the study to ensure compliance with the relevant data protection legislation.

14.2 Data Recording and Record Keeping

The registration section of the Case Report Form (CRF) will include:

- Site code
- Participant full name
- Participant address or email address

Participant phone number

- Participant age (at study enrolment)
- Participant gender
- Date of consent of participant

The clinical part of the CRF will include:

- Whether the participant has been recruited to the study previously
- Number of skin lesions being excised

- o Number of skin lesions being excised that are ulcerated (if more than one ulcerated lesion, then the patient and researcher should agree on an index lesion for the OASIS study)
- o Suspected type of index skin cancer (clinical diagnosis) – to be confirmed on histology
- o Site of procedure(s)
- o Size of index skin cancer (mm)
- o Size of index tumoral ulceration (mm)

Participants and the clinicians performing the procedure will be asked whether they would agree for the participant to be randomised to no antibiotics, topical treatment eg. InadineTM dressings, a short course of antibiotics or a longer course of antibiotics in a future RCT.

- o Whether InadineTM dressing applied to wound
- o Whether topical antibiotics applied to wound
- o Whether oral antibiotics prescribed

Type of procedure

All data and personal information will be stored in locked filing cabinets in fireproof locations in restricted areas.

Data processing and data sharing arrangements will be documented in the Statement of Activities between each participating site and the sponsor. Data from the clinical part of each CRF, together with the participant's name, address and phone number should be returned to the CTR for data entry within four weeks of the visit via an encrypted secure file transfer service in accordance with the General Data Protection Regulation and Data Protection Act 2018. The CRF is to be retained at the local site. In accordance with the principles of GCP, the PI is responsible for ensuring accuracy, completeness, legibility and timeliness of the data reported to the CTR. Data received by the CTR from participating study sites will be checked for missing, illegible or unusual values (range checks) and consistency over time. If missing or questionable data are identified, a data query will be raised on a data clarification form. The data clarification form will be sent to the relevant participating site. The site shall be requested to respond to the data query on the data clarification form. The case report form pages should not be altered. All answered data queries and corrections should be signed off and dated by a delegated member of staff at the relevant participating site. The completed data clarification

form should be returned to the CTR and a copy retained at the site in a site file along with the participants' CRFs. The CTR will send reminders for any overdue data. It is the site's responsibility to submit complete and accurate data in timely manner.

Each participant's name, address or e-mail address and phone number will be shared with the CTR so that the follow-up questionnaires can be sent from the CTR where the data will be collected. The participant's phone number may be used to obtain missing information. All paper data and personal information will be stored in locked filing cabinets in fireproof locations in restricted areas. Electronic data will be stored on university servers, accessed via password protected, encrypted, firewall protected and backed up computers. All personal data will be confidentially destroyed at the end of the study. Once the participant's data has been collected they will be allocated a unique participant identification number (PID, assigned sequentially as each patient is registered). The PID will be used for the purpose of data analysis. The data generated by the study will be analysed by the CTR team led by [name], Research Associate in Statistics and [name], Research Fellow/ Senior Trial Manager.

14.3 Participant Confidentiality and Data Protection

All investigators and study site staff must comply with the requirements of the General Data Protection Regulation and Data Protection Act 2018 with regards to the collection, storage, processing and disclosure of personal information and will uphold the Act's core principles. All research staff and delegated site staff will be trained in data protection and data management.

14.4 Record Storage and Retention

Essential documents pertaining to the trial shall not be destroyed without permission from the Sponsor. The TMF and ISF containing essential documents will be kept for a minimum of 5 years after completion of study. The CTR will send the Trial Master File to the sponsor at end of study for archiving. Documents (paper and electronic) will be retained in a secure location during and after the study has finished. Each PI at any participating site will archive the essential documents generated at the site for the agreed archiving period.

Study data	CRF	Wound 'selfies'	Questionnaire
Demographic data	X		
Procedure data	X		
Follow up data			X
Skin swab result (UHW pts only)	X		
Photos of infected wounds		X	

15 Protocol/GCP non-compliance

The Principal Investigator will report any non-compliance to the study protocol or the conditions and principles of Good Clinical Practice to the CTR in writing as soon as they become aware of it.

In the event that a serious breach of the protocol or GCP is suspected, this must be reported to the sponsor immediately. The sponsor will investigate the breach and any preventative and or corrective actions required will be undertaken by the research team. REC will be informed by the Chief Investigator if a serious breach is identified.

16 End of Study definition

The follow up period will continue for 4 weeks after the last participant's last data item.

The end of the study is defined as the date of final data capture to meet the study endpoints. In this case end of study is defined as the date on which the last participant is contacted by telephone four weeks after registration.

CI or a delegate will notify the main REC of the end of a clinical study within 90 days of its completion or within 15 days if the study is terminated early.

17 Regulatory Considerations

17.1 Ethical and governance approval

The study will be assessed for governance and legal compliance by HCRW. Once all checks are satisfied HCRW will issue HRA/HCRW approval. The study should not commence at any site until local confirmation of capacity and capability is also received via email by the CI/ PI. Before the start of the study, approval will be sought from HCRW and REC for the protocol, informed consent forms and other relevant documents. Amendments that require review by HCRW and REC will not be implemented until approval is granted. The CI (or delegate) should submit any amendments to their National Coordinating Unit, HCRW. The HCRW Permissions Service will assess and approve the amendment.

17.2 Data Protection

The sponsor will act to preserve participant confidentiality and will not disclose or reproduce any information by which participants could be identified, except where specific consent is obtained. Data will be stored in a secure manner and will be registered in accordance with the General Data Protection Regulations 2018.

17.3 Indemnity

This is an NHS-sponsored research study, and the NHS indemnity scheme therefore applies. If there is negligent harm during the study when the NHS body owes a duty of care to the person harmed, NHS indemnity covers NHS staff, medical academic staff with honorary contracts, and those conducting the trial. The NHS indemnity scheme does not cover non-negligent harm.

17.4 Study sponsorship

Cardiff and Vale University HB will act as Sponsor for the OASIS study. The HB shall be responsible for ensuring that the study is performed in accordance with the following:

- Conditions and principles of Good Clinical Practice.
- Declaration of Helsinki (1996).
- UK Policy Framework for Health and Social Care Research (2017).
- The Data Protection Act 1998.
- Other regulatory requirements as appropriate.

The Sponsor has/will be delegating certain responsibilities to Cardiff University (CTR), the CI, PIs, host sites and other stakeholder organisations as appropriate in accordance with the relevant agreement that is informed by regulation and study type.

17.5 Funding

The UK DCTN has awarded £10,000 for this study. Dermatology Forum for Wales has awarded £500 towards this study. The shortfall of £1,055.25 will be met by CAVUHB Dermatology Department Research Fund.

18 Quality Control and Assurance

Appendix 1: Questionnaire

Since you left hospital after having surgery.... Response categories

1 Was there redness spreading away from the wound? (erythema/cellulitis) Not at all / A little / Quite a bit / A lot

2 Was the area around the wound warmer than the surrounding skin? Not at all / A little / Quite a bit / A lot

3 Was any part of the wound leaking fluid? Not at all / A little / Quite a bit / A lot

a) Was it clear fluid? (serous exudate) Not at all / A little / Quite a bit / A lot

b) Was it blood-stained fluid? (haemoserous exudate) Not at all / A little / Quite a bit / A lot

c) Was it thick and yellow/green fluid (pus/purulent exudate) Not at all / A little / Quite a bit / A lot

d) I do not know

4 Have the edges of any part of the wound separated/gaped open on their own accord? (spontaneous dehiscence) Not at all / A little / Quite a bit / A lot

a) Did the skin separate? Not at all / A little / Quite a bit / A lot

b) Did the deeper tissue separate? Not at all / A little / Quite a bit / A lot

c) I do not know

5 Has the area around the wound become swollen? Not at all / A little / Quite a bit / A lot

6 Has the wound been smelly? Not at all / A little / Quite a bit / A lot

7 Has the wound been painful to touch? Not at all / A little / Quite a bit / A lot

8 Have you had, or felt like you have had, a raised temperature or fever? Not at all / A little / Quite a bit / A lot (fever <38°C)

9 Have you sought advice because of a problem with your wound, other than at a routine planned follow-up appointment? Yes / No

If yes, please tell us who you sought advice from:

a) A doctor or nurse at the GP surgery/medical centre/walk-in centre Yes / No

b) A doctor or nurse at the hospital Yes / No

c) A midwife or health visitor Yes / No

d) Another health advisor Yes / No

Please describe who the other health advisor was _____

10 Has anything been put on the skin to cover the wound? (dressing) Yes / No

If yes,

a) Was this done by a doctor or nurse at the GP surgery/ medical centre/walkin centre? Yes / No

b) Was this done by a nurse/midwife/health visitor at home? Yes / No

c) Was this done by you/your partner/friend/family member? Yes / No

d) Was this done by a doctor/nurse/midwife at the hospital? Yes / No

e) Please describe what was put on to cover the wound _____

11 Have you been back into hospital for treatment with a problem with your wound? Yes / No

12 Have you been given antibiotics for a problem with you wound? Yes / No / Don't know

If yes,

a) Were the antibiotics given as tablets/liquid? Yes / No / Don't know

b) Were the antibiotics given via drip? Yes / No / Don't know

If you know the name of the antibiotic(s) you have taken, please write it here _____

13 Have the edges of your wound been deliberately separated by a doctor or nurse? Yes / No / Don't know

14 Has your wound been scraped or cut to remove any unwanted tissue? (debridement of wound) Yes / No / Don't know

15 Has your wound been drained? (drainage of pus/abscess) Yes / No / Don't know

16 Have you had an operation under general anaesthetic for treatment of a problem with your wound? Yes / No / Don't know

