5.1 Primary objectives

- To determine the proportion of participants developing SSI following excision of ulcerated skin tumours in three Dermatology Departments: University Hospital of Wales, Cardiff; Churchill Hospital, Oxford and Queen Elizabeth Hospital, Birmingham

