5.3 Primary outcomes measure

The main objective is to determine the proportion of participants with SSI within four weeks of surgery. The research team will arrange to contact the participant four weeks after the procedure via a validated questionnaire (see details below) to determine whether they had any concerns about post-operative infection and what action was taken. SSI is broadly defined as the presence of one of the following criteria associated with the wound: abscess, cellulitis, discharge, delayed healing, discolouration, friable granulation tissue, unexpected pain/tenderness, pocketing at base of wound, abnormal smell, wound breakdown.¹² A systematic review has acknowledged the use of several different classifications for SSI and the lack of a standardised tool for diagnosing SSI.¹³ In response to this, Macefield *et al.* have developed a single patient and observer measure for post-discharge SSI assessment and have given us permission to use the tool in this study.¹⁴

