10.2 Lost to follow up

1. Participants will be identified as lost to follow up if we are unable to contact them four weeks after their procedure.
2. Measures that we will take to try and get the missing information include three attempts to telephone or text the participants. If we are unable to contact the participant by telephone then and we will also send them a letter asking them to contact the study centre.'

11 Study procedures

The following are to be recorded before skin surgery on the CRF:

- Whether the participant has been recruited to the study previously
- Number of skin lesions being excised
- Number of skin lesions being excised that are ulcerated (if more than one ulcerated lesion, then the patient and researcher should agree on an index lesion for the OASIS study)
- Suspected type of index skin cancer (clinical diagnosis) – to be confirmed on histology
- Site of procedure(s)
- Size of index skin cancer (mm)
- Size of index tumoral ulceration

Participants and the clinicians performing the procedure will be asked whether they would agree for the participant to be randomised to no antibiotics, topical treatment eg. Inadine™ dressings, a short course of antibiotics or a longer course of antibiotics in a future RCT.

The following will be recorded after skin surgery on the CRF:

- Type of procedure
- Whether Inadine™ dressing applied to wound
- Whether topical antibiotics applied to wound
- Whether oral antibiotics prescribed

A questionnaire [Appendix 1] will be sent to participants by post or email at four weeks. A stamped-addressed envelope will be sent with the questionnaire for the reply if required.

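### The questionnaire behind the primary outcome does not say which wound it asks about, so SSI after excision of the ulcerated lesion can be over- or undercounted in participants with several excisions

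*Combined protocol and SAP*

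**What the plan says.** Section 5.1 sets the target: "To determine the proportion of participants developing SSI following excision of ulcerated skin tumours in three Dermatology Departments". Section 5.3 adds the time frame ("The main objective is to determine the proportion of participants with SSI within four weeks of surgery"), names the four-week questionnaire as the source, and treats any one of a list of wound signs as enough for SSI. The synopsis likewise says the outcome is identified by questionnaire.

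The form in Appendix 1 opens with "Since you left hospital after having surgery". Its items then refer to a single unnamed wound, as in "Was there redness spreading away from the wound". It has no space for a site and no item asking which wound had a problem.

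Sections 11 and 14.2 allow for several excisions. The CRF records how many lesions are excised and how many are ulcerated, with the instruction "if more than one ulcerated lesion, then the patient and researcher should agree on an index lesion for the OASIS study". Tumour type, tumour size and ulceration size are recorded for the index lesion. The site field is not labelled in that way and covers all procedures. Section 8.2 does not exclude people having several excisions.

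On analysis, section 12.4 says "For each analysis, only patients with relevant evaluable data will be analysed", and section 13.1 specifies a proportion with a 95% confidence interval. Neither says which wound counts.

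**The concern.** The baseline data describe one identified lesion, while the outcome form identifies none. A participant with two wounds might report trouble in either one, or answer only about the one that bothered them more. The first would add infections that do not belong to the index lesion. The second could miss an infection in it. Section 4 says this proportion is needed to set the sample size of a future randomised trial in ulcerated skin cancers, so an error in it would carry into that trial. The confidence interval would not show it, because misattribution is not sampling error.

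**Working it through.** **Can anything else in the plan tie an answer to the index wound?**

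- The index agreement in section 11 is required only when more than one lesion is ulcerated, and the agreed lesion is not shown on the form four weeks later. With one ulcerated and one non-ulcerated excision, no agreement is called for.
- Wound photographs are collected to judge feasibility and are not analysed (section 11.1).
- Telephone contact is for non-response (section 10.2) or missing information (section 14.2). A completed form about another wound looks complete.
- Sections 12.4 and 13.1 give no counting rule.

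So nothing described in the plan resolves the attribution.

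**Planned precision.** Section 12.1 anticipates 10% SSI with 283 evaluable participants and states an interval of 6.9% to 13.5%. The normal-approximation half-width is 1.96 × √(0.10 × 0.90 / 283) = 3.5 points, giving 6.5% to 13.5%. Wilson's method gives 7.0% to 14.0%. The stated lower limit was not reproduced together with the upper one. That is a separate matter and does not affect this point. I use 3.5 points as the yardstick.

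**Illustration.** Inputs:

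- Index-wound rate 10%. Section 12.1 gives this as a rate in participants; reading it as an index-wound rate is an assumption.
- f, the share with one extra wound: not in the documents; assumed 10% to 30%, middle value 20%.
- p, the SSI risk in the extra wound: 2% to 8%, the range section 4 quotes for all skin cancer excisions; middle value 5%.
- Wounds in the same person independent: assumed.

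Overcount, if a problem in either wound is reported: (1 − f) × 0.10 + f × [1 − 0.90 × (1 − p)], a shift of f × 0.90 × p.

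Undercount, if half of these participants answer only about the other wound: (1 − f) × 0.10 + f × (0.5 × 0.10 + 0.5 × p), a shift of −f × 0.5 × (0.10 − p).

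| Case | f | p | Observed | Shift (points) | SSIs in 283 |
|---|---|---|---|---|---|
| Overcount, low | 10% | 2% | 10.18% | +0.2 | +0.5 |
| Overcount, middle | 20% | 5% | 10.90% | +0.9 | +2.5 |
| Overcount, high | 30% | 8% | 12.16% | +2.2 | +6.1 |
| Undercount, low | 10% | 8% | 9.90% | −0.1 | −0.3 |
| Undercount, middle | 20% | 5% | 9.50% | −0.5 | −1.4 |
| Undercount, high | 30% | 2% | 8.80% | −1.2 | −3.4 |

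With f = 0 both shifts are zero. If the second wound is also ulcerated and carries a 10% risk, then at f = 20% the undercount is 0.20 × 0.5 × (0.10 − 0.10) = 0 and the overcount is 0.20 × 0.90 × 0.10 = 1.8 points.

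**Cost in precision of a single-excision analysis.** Keeping 283 × (1 − f) participants leaves 255, 226 or 198 for f = 10%, 20% or 30%. The half-widths at 10% SSI are 3.7, 3.9 and 4.2 points.

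**The case against.** The best reply is that participants will usually know which lesion is meant. They are invited because of an ulcerated lesion. With one such lesion there is only one candidate, and with several they have agreed the index lesion with the researcher. The CRF records index type and size for everyone, so an index lesion exists on paper in each case. Appendix 1 may also be only the item list: a cover letter, the information leaflet or the post-operative leaflet could name the lesion, and none of these is in the documents. This makes a wrong-wound answer less likely. It does not replace a named site on the form or a counting rule in the analysis.

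The illustration can fairly be challenged too. The share with several wounds is assumed. Infections in one person's wounds are probably positively correlated, which would shrink the overcount. The two errors also partly cancel.

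A reader might infer that the affected participants cannot be found. They can, because the lesion count on the CRF identifies everyone who could be affected; only the individual misdirected answers stay hidden. A reader might also infer that the form's lack of an end date, an onset date or a completion date lets many late events in. The form goes out at four weeks, so this is probably a small effect, and the documents give nothing from which to compute it.

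**Conclusion.** The point holds as a gap in how the primary outcome is measured, confined to participants with more than one excision. The direction of the error is not known, and its size cannot be determined from the documents. In the middle case (20% with one extra wound, 5% risk in it, independent wounds) the shift is +0.9 points if either wound is reported, or −0.5 points if half answer about the other wound. Both are well inside the 3.5-point half-width. At the low end the shift is trivial.

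A reader might go further and conclude that the SSI estimate is materially biased or unfit for planning the trial. The documents do not support that: they give neither the share with several wounds nor any sign of how such participants would answer, and participants with a single excision are unaffected. This is a cheap improvement worth making, not a flaw that invalidates the design.

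**What to change.** 1. Leave the questionnaire items, which section 5.3 describes as validated, unchanged.
2. On the CRF, label the index (ulcerated) site for every participant with more than one excision, including those with only one ulcerated lesion.
3. Print that site in a header on the questionnaire.
4. State in section 12.4 or 13.1 that the primary proportion counts SSI in the index wound. This also settles whether a second ulcerated wound counts.
5. Report a sensitivity analysis in single-excision participants, using the lesion counts already collected.

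The cost is a minor amendment, one CRF label, individually headed forms and one extra analysis. The constraint is timing. Section 14.2 allows clinical CRF data to reach the trials centre up to four weeks after the visit, which is when the questionnaire is due out. For participants with several excisions, the index site should therefore travel with the contact details in time for the mailing, not at the four-week limit. Onset and completion dates would be optional additions and are not needed for this fix. If a cover letter already names the lesion, the work reduces to documenting that, adding the counting rule and running the sensitivity analysis.
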